Individuals meeting inclusion and exclusion criteria will be invited to participate in the study protocol, consisting of a battery of neuroimaging tasks completed prior to and following completion of treatment. Individuals choosing to participate in the study will be asked to lie in an MRI scanner, located at the Fralin Biomedical Research Institute at Virginia Tech Carilion in Roanoke, VA, and play simple games consisting of viewing objects on a digital screen and making choices by pressing handheld buttons. The scanner detects regional cerebral blood flow accompanying changes in brain activation when subjects are perceiving emotional or reward-related stimuli. Subjects will be asked to participate in three tasks of this nature during the scanning session, depending on their comfort level and time available. Following the initial fMRI scanning session, participants will begin treatment (TMT or PE). Following completion of treatment, participants will undergo the above-described fMRI scanning procedures a second time.

PROCEDURES:

All research activities will be conducted by Salem VAMC research staff members at Fralin Biomedical Research Institute at Virginia Tech Carilion (FBRI) and/or Salem VAMC. The PI or

a clinically experienced senior staff member will accompany all subjects with PTSD throughout their participation in the study.

I. Recruitment

Veterans may learn of this study by being informed by residential clinical staff, receiving a letter from research staff at the Salem VA Medical Center (attached), word of mouth, or when inquiring about residential treatment at the Salem VA Medical Center. During the initial patient screening phone call for the PTSD residential unit, the VA staff member will also inform the patient of the study. If a veteran is interested in participating in research, study staff will contact him/her by phone to provide information about the study and conduct initial eligibility screening. In addition, letters will be mailed to Veterans who have expressed interest in the study. This letter (attached) will provide the Veteran with the contact information for study staff. At the request of clinical PTSD RRTP staff, a letter (see attached) including a description of the study and contact information for study staff will be provided to the PTSD RRTP clinical coordinator for the purpose of including it in each Veterans' clinical welcome packet.

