Written informed consent will be obtained after the veteran is admitted to the Salem VA residential PTSD unit. Upon arriving at the Salem VA PTSD residential unit, individuals will again be given an overview of the study, including a basic description of the study design, and any questions they have will be answered. As part of the intake process within the unit, a variety of clinician-administered and self-report measures are completed to evaluate psychiatric symptoms and current psychosocial functioning, including the PTSD Checklist (PCL-5); Beck Depression Inventory (BDI-II); Posttraumatic Cognitions Inventory (PTCI); five facets of mindfulness; Insomnia Severity Index (ISI); Acceptance and Action Questionnaire (AAQ-2); and Disturbing Dreams and Nightmare Severity Index (DDNSI), etc (see attached for samples). S/he will be asked to consent to the use of the audio recordings of his/her clinical interviews during the research intake screening (SCID-5-RV & CAPS-5), and of his/her individual therapy sessions, so that the reliability of assessment procedures and treatment fidelity can be evaluated. In addition, s/he will be asked to give permission for research staff to access intake assessment information and medical record history, in order to further evaluate eligibility criteria for the study.

Interested veterans will also be asked to complete a pre-consent MRI screening form (attached) over the telephone during their initial phone screen with study staff. If contraindications to MRI involving potential metal are identified (e.g. shrapnel, medical devices, etc.), veterans will be instructed to request a written note from their medical provider stating that any metal in their body is MRI safe. A radiologist from Salem VAMC may evaluate the safety of the veteran to participate in the study, should he or she desire to participate. If a participant is ineligible to participate in the MRI portion of this study, they may participate in the rest of the study and complete the tasks outside of the scanner.

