Individuals who remain eligible for the study following clinical intake assessments, research intake assessments, review of medical record and assessment for contraindications to MRI will be invited to participate. Once the participants complete all pre-treatment study procedures, all participant data will fall under intention-to-treat analysis, where dropouts and non-compliant participants may be followed up on with post-treatment assessments and follow-up assessments as with all other

participants. Veterans who are found to not meet inclusion criteria following pre-treatment assessment may be unenrolled from the study at the discretion of study staff. All Veterans who are removed from the study will be paid for all study procedures completed to that point.

Veterans who may be eligible for Neuroscience of Social Behavior (PC-0002) study will be asked to complete a Release of Information form to share their contact information with PC-0002 study staff. A copy of relevant de-identified assessment data (see attached list) may also be released to the PC-0002 staff once written informed consent has been obtained by them from the Veteran.

The research staff will explain the study to the veteran and will answer any questions he/she may have prior to obtaining written informed consent.

Veterans will be assured that their choice to participate, or not, will have no effect on their treatment, clinical care or relationship with their clinician.

II. Assessment and Intervention

Initial Visit: Consent and Pretreatment Procedures

After written informed consent has been obtained, participants will begin study procedures.

Participants will complete pretreatment interviews, including the CAPS-5, SCID-5-RV with a trained clinical interviewer prior to beginning treatment.

Participants will complete the study questionnaires on paper during the first week at FBRI and/or at the Salem VA Medical Center (questionnaire battery including, for example, PCL, SAS-SR, AQ, ITS, etc.). Additionally, acceptability of treatment will be assessed through measures of treatment credibility and satisfaction after three weeks of treatment and the end of treatment, respectively.

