The participant will be transported via VA vehicle or their own transportation arrangement from the PTSD residential unit at the Salem VAMC to the Human Neuroimaging Lab at the Fralin Biomedical Research Institute (FBRI) at Virginia Tech Carilion for the pre-treatment fMRI scanning/task visit. If the participant chooses to be transported via VA vehicle, they will be accompanied to the FBRI by trained research staff member who has been VA-approved to transport veterans.

Identifiable data (MRI screening form and Informed Consent form) will be transported by authorized study staff outside of the VA to the Fralin Biomedical Research Institute at Virginia Tech Carilion during the fMRI pre- and post- treatment scanning visits via a secure, locked VA document bag in the VA vehicle. This identifiable information will not be stored or housed off-site. All identifiable information will return directly to the Salem VAMC in the VA vehicle with the authorized study staff following the scanning visit(s).

Following consenting procedures and transporting the participant via VA vehicle to the FBRI, study staff will review safety issues related to MRI with the subject and answer any questions the participant may have. The primary procedure for this portion of the study is an MRI scan. The

MRI scanner is a 3.0 T scanner, approved for clinical use by the FDA. For subjects with PTSD, a clinically trained staff member will be available throughout the experiment to assist the veteran if he/she becomes agitated, frightened, or hostile.

In an effort to reduce the possibility that subjects will be adversely affected by the scanner noise or the visual or auditory stimuli, subjects will be shown sample stimuli to be used in the task (see attached). Before they are presented, the experimenter will briefly describe the sample stimuli and inform subjects that they can decide either to view or not view the stimuli. In addition, short clips of representative scanner sounds and volume will be played prior to the participant entering the scanner.

After being presented with the representative stimuli and hearing scanner sounds, participants will again be asked whether they want to continue with the study. They will be informed that they still will be compensated for their time if they choose not to complete the scan. Should the participant indicate they wish to discontinue the study, the study will be terminated at no penalty to the subject.

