At each fMRI scanning session, the subjects will lie still for up to 35 minutes while in the scanner. Individuals will have the opportunity to get into and out of the scanner between each task described below. As with conventional scanners, the subject in the scanner will be in voice-communication with a technician, clinically experienced staff member, or investigator via an intercom and will have an emergency squeeze bulb in case he/she wishes to be withdrawn.

Participants will be asked to perform some or all of the following tasks depending on their comfort and time available. For all the scanning tasks, participants will view a computer display positioned at one end of the scanner by looking into a mirror positioned above their head. They will also use handheld buttons similar to a computer mouse to make choices during the games. If the participant is not MRI-eligible, they will complete these tasks on desktop computers outside of the scanner.

Task 1: Interpersonal interaction: The participant will play an exchange game with a human partner who has also joined the study, or a 'computer' partner that has been preprogrammed to play the game. The experience of the game will be similar to a standard, commercial video game, except with much simpler images. While playing the game, subjects will view stimuli representing their options and choices (e.g., an unmarked card and a slider bar indicating a choice of \$10). Choices will be made by pressing buttons on a button box. Subjects will be compensated, in part, based on their earnings in the exchange game in order to incentivize performance. The duration of this task is approximately 30 minutes.

Task 2: Cue / emotional-reactivity task: This task assesses neural signals associated with responses to simple visual stimuli. Participants will view or hear generic stimuli (e.g., colors, words, symbols, sounds or images drawn from standard stimulus sets such as the International Affective Picture System; IAPS, Lang et al., 1995; International Smoking Images, Gilbert; International Affective Digitalized Sound System, IADS, Bradley & Lang, 1999) as they are asked to make evaluative judgments (e.g., preference, duration, valence ratings) or passively view the stimuli. The duration of this task is approximately 15 minutes.

Task 3: Social Status/Aggression task: During this task, the participant will play an exchange game with a human partner who has also joined the study, or a 'computer' partner that has been

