For each task, participants will be compensated according to a structured payment plan (see Table 1 below). Payment is based on the modal time required to complete the scanning session at a rate of \$30/hour if completed inside the scanner and \$15/hour if completed outside of the scanner. Additionally, for the interpersonal interaction task (Task 1) and the social status task (Task 3), participants will be compensated based on their earnings in the exchange game in order to incentivize performance in addition to the hourly rate. Participants may also earn between \$20 to \$75 based on their performance on two of the MRI tasks.

Transportation compensation:

Participants will either be transported from the Salem VAMC to the FBRI to participate in the fMRI visits via a state vehicle or their own transportation arrangement. Parking at FBRI is free, so no parking compensation is required. The participants will be compensated a flat rate of \$10 for roundtrip transportation. This rate is included in the total compensation for the fMRI visit;

however, in the event that a participant chooses to end an fMRI session early, they will still receive the full \$10 transportation compensation.

Incomplete procedures/tasks:

Should participants choose to end any procedure early without completing it, they will be paid \$15/hour for time spent, up to the scheduled payment for that procedure. As noted above, in the event that a participant chooses to end an fMRI session early without completing it, they will still receive the incorporated (and previously IRB approved) \$10 compensation for transportation.

Unforeseen scanner-related delays:

Should participants encounter unusually long fMRI delays due to technical problems outside the control of the study staff, they may be paid \$15/hour, at the discretion of study staff, for the duration of the delay to compensate for their time.

Participation bonus:

Participants can earn up to \$40 in additional bonuses across posttreatment and follow up procedures conducted over the telephone, and those who participate in all portions of the study will receive a participation bonus of \$50.

Participants can expect to earn a minimum of \$170 for completing all portions of the study and a maximum of \$700.

Payment Structure

Pretreatment CAPS w/LEC	\$30
Pretreatment SCID & SCID-MDE	\$30
Pretreatment questionnaires	\$30
Pretreatment fMRI	\$45/90 (depending on in/out of scanner)

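### Membership of the clinical (CAPS-5/SAS-SR) analysis set is tied to MRI scanning in two places, although the clinical comparison does not need a scan

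*Protocol*

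**What the plan says.** **Entry to intention to treat.** Protocol, I. Recruitment: "Once the participants complete all pre-treatment study procedures, all participant data will fall under intention-to-treat analysis". From that point, dropouts and non-compliant veterans may be followed up like everyone else.

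**The scan visit is a pre-treatment procedure.** Study Design has treatment begin after the first scanning session. The visit is described under Initial Visit: Consent and Pretreatment Procedures, and the payment table has a pre-treatment fMRI line.

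**The tasks are optional.** Initial Visit: "Participants will be asked to perform some or all of the following tasks depending on their comfort and time available".

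**The choice offered before scanning.** After sample stimuli and scanner sounds, "participants will again be asked whether they want to continue with the study". Then: "They will be informed that they still will be compensated for their time if they choose not to complete the scan". Then: "Should the participant indicate they wish to discontinue the study, the study will be terminated at no penalty to the subject".

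**Veterans who cannot have MRI.** I. Recruitment: "they may participate in the rest of the study and complete the tasks outside of the scanner". Initial Visit gives the desktop version for veterans who are not MRI-eligible. Subject Exclusion Criteria also sends them to behavioural-only tasks, but then lists MRI contraindications among the exclusions applied to all participants at analysis.

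**SAP.** CAPS-5 and SAS-SR are the primary outcomes, tested by a Time x Treatment interaction with age as covariate. No analysis population and no missing-data rule is given.

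**The concern.** Aim 1 asks whether TMT improves PTSD symptoms and interpersonal function. CAPS-5 and SAS-SR answer that without a scan; only the mediation aim needs imaging. Yet two rules let scanning decide who is counted in the clinical comparison: completion of every pre-treatment procedure, and the analysis-stage exclusion for MRI contraindications.

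Three things are at stake.

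- **Population.** Willingness to undergo a noisy, confined scan and view emotional images is plausibly related to PTSD severity. Initial Visit itself provides for veterans who become agitated or frightened. A set filtered this way is narrower than the treatment-seeking veterans of Aim 1.
- **Timing.** The unit runs one arm at a time, and standard consent follows admission. A loss at the scan can therefore come after the arm is fixed, so the set is not all assigned veterans.
- **Data.** Clinical scores that exist, or could be collected, may go unused.

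**Working it through.** **1. Can a veteran who follows the protocol fail the intention-to-treat rule?**

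- I. Recruitment requires completion of *all* pre-treatment procedures.
- The scan visit is one of them (Study Design, Initial Visit, payment table).
- Initial Visit allows only some of the tasks to be done, according to comfort and time.

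A veteran who does one task of three has complied with Initial Visit but may not meet the rule in I. Recruitment. This conflict needs no assumption about refusal rates.

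**2. What happens to an MRI-eligible veteran who declines the scan?**

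- Initial Visit asks about continuing the study, not the scan.
- For declining the scan it states payment but not study status.
- For discontinuing the study it states termination.
- The desktop route is given only for veterans who are not MRI-eligible.
- Follow-up commits to assessing those who leave during treatment. I. Recruitment extends follow-up to dropouts once pre-treatment procedures are complete. Neither clearly covers a veteran who stops before that point.

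The status of this veteran is undefined.

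**3. What happens to a veteran with an MRI contraindication?**

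- Conduct: stays in, with tasks outside the scanner (Subject Exclusion Criteria, I. Recruitment, Initial Visit).
- Analysis: excluded (Subject Exclusion Criteria).

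Read literally, this veteran is treated, assessed and paid, then left out of every analysis, including the clinical one.

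**4. Size.**

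The plan's own figure reproduces (Sample Size):

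- 2 × 44 = 88 completers
- 88 × 1.5 = 132 enrolled
- Allowed loss: 132 − 88 = 44, and 44/132 = 33.3%

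The documents give no rate of scan refusal, partial completion or MRI contraindication. As an illustration, assume a combined rate f among the 132:

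| f (assumed) | 132 × f | Share of the 44 allowed | Completers if the loss is extra: 132 × (1 − f) × 2/3 |
|---|---|---|---|
| 5% | 6.6 | 15% | 83.6 |
| 10% | 13.2 | 30% | 79.2 |
| 20% | 26.4 | 60% | 70.4 |

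The 1.5 factor covers everyone who fails criteria or does not finish. If it already includes these veterans, the 88 is unaffected. The last column is the other extreme, where the loss comes on top of the one-third. The documents do not say which applies. No stated number in the plan changes.

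**The case against.** The strongest reply is that the plan leaves a term undefined and no loss of veterans is established. Several points in it stand.

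- **A reader might infer that stopping at the scan ends participation in the whole study.** The documents do not say so. Termination applies to a veteran who wishes to discontinue the study, and the preceding sentence deals with not completing the scan separately. Cost/Compensation provides that "in the event that a participant chooses to end an fMRI session early without completing it, they will still receive" the transport payment, with no removal stated. Risks & Benefits takes a claustrophobic participant out of the scanner, and says nothing of the study. Loss of these veterans is possible but not stated.
- **A reader might infer that veterans with metal contraindications are kept while scan-averse veterans are lost.** That contrast holds for conduct only. The analysis-stage exclusion removes the first group too.
- **A reader might assume that both primary outcomes are already in hand at the scan.** This is not shown for SAS-SR. Questionnaires are completed in the first week, at the imaging site or the hospital, with no order fixed relative to the scan.
- **The planned loss may absorb the number.** This is true, but it protects sample size and not the make-up of the set.
- **The scan precedes treatment and is the same in both arms.** This also stands: no route to differential loss is shown, so the consequence is mainly one of population and efficiency.

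The reply does not dispose of the conflict between requiring all procedures and making tasks optional, the contradiction between keeping MRI-ineligible veterans and excluding them at analysis, or the SAP's silence on who is analysed.

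**Conclusion.** The point holds as a problem of analysis-set definition. Scanning can decide membership of the clinical set through two rules, neither needed for CAPS-5 or SAS-SR, and nothing in the SAP overrides them. Applied literally, they can remove consented and otherwise eligible veterans after the arm on offer is fixed. That narrows the population for Aim 1 and can waste primary-outcome data.

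The size is unknown. The 7 to 26 veterans shown rest on an assumed 5% to 20% and may lie wholly within the 44 losses already allowed. A link between scan tolerance and severity is plausible but not shown in the documents. A reader might go further and conclude that the treatment comparison is biased between arms; the documents give no evidence of unequal loss. The matter should be fixed, but it does not by itself invalidate the comparison.

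**What to change.** 1. **I. Recruitment and the SAP.** Define the clinical intention-to-treat set as consented, eligible veterans with an assigned arm and pre-treatment CAPS-5 and SAS-SR, with no condition on scan or task completion. State that SAS-SR is collected whether or not the scan goes ahead, so that the baseline condition does not bring the scan back in.
2. **Subject Exclusion Criteria.** Restrict the MRI-contraindication exclusion, and any scan-completion condition, to the imaging mediation set, and reconcile this with I. Recruitment and Initial Visit.
3. **Initial Visit.** Replace the single question with two choices: stop the scan, be offered the desktop tasks and remain in the study; or withdraw from the study.
4. **Reporting.** The SAP is largely in the past tense, so the analysis may already be done. Report by arm how many consented veterans were left out at this step and why.

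The cost is mainly wording, plus one item on the scan-visit form. The desktop tasks and their payment rate already exist. The clinical and imaging sets will differ in size, and some veterans brought into the clinical set may lack post-treatment scores, so the SAP would need to say how they are handled.

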Male and female veterans of all ethnicities will be sought to participate. All participants must meet the following criteria during intake or analysis: 1) be between 18 and 64 years of age; 2) meet DSM-5 criteria for current Post Traumatic Stress Disorder, as assessed by study staff using the Clinician Administered PTSD Scale-5 (CAPS-5); 3) be fluent in English; 4) have vision corrected to be able to see a computer display clearly; 5) be able to provide informed consent and be able to follow verbal or written instructions; 6) assessed as not a significant harm to self or others.

SUBJECT EXCLUSION CRITERIA

All participants admitted to the unit will be allowed to partake in the study. Those with contraindications to the fMRI will complete behavioral only tasks. The following exclusion criteria will be applied to all participants during analysis: younger than 18 or older than 65; self-reported PTSD symptoms for less than six months; diagnosed seizure disorder; history of stroke; Cushing's syndrome; history of moderate to severe traumatic brain injury (TBI); electroconvulsive therapy within 5 years; history of chemotherapy for cancer; contraindications to fMRI; current pregnancy; diagnoses of schizophrenia, schizoaffective disorder, delusional disorder, organic psychosis, bipolar disorder, or depressive disorder with psychosis as assessed with SCID-5-RV (and not stabilized or in remission); symptoms meeting criteria for a substance use disorder within the previous 30 days (assessed through SCID-5, Alcohol Use Disorders Identification Test score > 8); meets criteria for acute psychiatric or medical admission; assessed as significant risk of harm to self or others; use of non-prescribed narcotics; acute cardiac difficulties (unless cleared by a cardiologist); psychotic disorders not otherwise specified assessed with SCID-5-RV; subjects using benzodiazepines (they will be given the opportunity to discontinue and must be off for at least two weeks prior to the beginning of the study); psychotropic medications must be stabilized for at least two weeks prior to the beginning of the study and remain stabilized throughout the entire duration of the study; if changed, the subject may be dropped from the study at the discretion of the research staff; positive drug tests during the course of the study will be grounds for disenrollment from the study. Given the high prevalence of psychotropic medication usage in

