PTSD, use of antidepressants or anxiolytics will not be an exclusion criterion. The subject may be dropped from the study at the discretion of the research staff.

USE OF SPECIAL/VULNERABLE POPULATION:

For this study, we will be recruiting individuals with PTSD. As individuals with mental illness can be a vulnerable population, we will take particular care to prevent undue coercion, protect the subjects' confidentiality, and obtain informed consent. All subjects will be informed of the purpose of the study, the potential value of the study to society, the lack of value to the subject personally, and potential risks to the subject. It will be explained to the subject that he or she is under no obligation whatsoever to participate, and that if he or she wishes to discontinue involvement at any time during the study he or she is free to do so without penalty. Individuals receiving treatment for PTSD or any medical treatment from the VA will be assured that their treatment will in no way be affected by their choice to participate or not participate, or their choice to withdraw at any time.

STUDY DESIGN:

This study consists of two primary treatment groups: 1) Trauma Management Therapy, comprised of exposure therapy (EXP) and social and emotional rehabilitation (SER) (N = 44), and 2) veterans receiving Prolonged Exposure Therapy (PE), comprised of exposure therapy plus skills-focues group therapy based in Acceptance and Commitment Therapy and informed by Dialectical Behavioral Therapy (EXP + ACT/DBT) (N = 44). All participants will be recruited within the Salem VAMC residential PTSD unit, a 13-bed facility offering residential care for veterans with PTSD. The unit will exclusively offer one of the two arms of treatment (EXP+SER or EXP+ACT/DBT) at any particular time, and the order of offering will be randomized across the year. Thus, assignment to treatment arm will be depend upon the treatment arm being currently offered.

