JUNE 1, 2023

EFFICACY AND NEURAL MEDIATORS OF
RESPONSE TO TRAUMA MANAGEMENT
THERAPY FOR PTSD
NCT03449576

Analysis of primary clinical outcome hypothesis for D2354-R “Efficacy and Neural Mediators of Response to Trauma Management Therapy for PTSD”

A regression approach was used to test the effect of treatment type (TMT, EXP+EDU) on both primary (CAPS-5 and SAS-SR) and secondary (PCL-5, AQ, ITS) outcome measures across Time (pre-treatment, post-treatment). The Time x Treatment interaction was be used to test whether TMT improves outcomes relative to EXP+EDU, and age was entered as a co-variate as the two treatment arms differed in age at baseline.

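### Whether a veteran who fails inclusion stays in is left to staff discretion, and exclusions are applied at analysis, usually with the arm evident; separately, the two age limits disagree

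*Protocol*

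**What the plan says.** **Protocol, Subject Inclusion Criteria.** "All participants must meet the following criteria during intake or analysis: 1) be between 18 and 64 years of age". The same list requires current PTSD on the CAPS-5.

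**Protocol, Subject Exclusion Criteria.** The section opens with "All participants admitted to the unit will be allowed to partake in the study" and continues "The following exclusion criteria will be applied to all participants during analysis". The age item in that list is "younger than 18 or older than 65".

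**Protocol, I. Recruitment.** Veterans who remain eligible after the intake work are invited. Once pre-treatment procedures are complete, all of a participant's data come under intention-to-treat. Then, a veteran who turns out at the pre-treatment assessment to fail inclusion "may be unenrolled from the study at the discretion of study staff". No criterion, deadline or record is attached to that discretion.

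**Protocol, Study Design.** "The unit will exclusively offer one of the two arms of treatment (EXP+SER or EXP+ACT/DBT) at any particular time". Assignment follows whichever arm is on offer, and the order of offering is randomised across the year.

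**Protocol, Consent Procedures.** Under the COVID-19 arrangements, the SCID and CAPS interviews are done by telephone or video before admission, to settle final eligibility.

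**SAP.** It names the outcomes, the Time x Treatment interaction and one covariate ("age was entered as a co-variate as the two treatment arms differed in age at baseline"). It does not say who is analysed.

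**The concern.** A criterion cannot be both mandatory and optional. Two veterans with the same sub-threshold CAPS-5 result could be handled differently, and nothing written would show why.

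In a trial with concealed individual allocation, discretion used before assignment would be mostly harmless. Here the arm is set by what the unit is running. In the standard pathway, consent follows admission and the research CAPS-5 and SCID-5 interviews follow consent. The finding of ineligibility is therefore reached on a 13-bed unit that is already delivering one identifiable programme. If veterans who fail a criterion tend to change by a different amount, keeping them in one arm and dropping them in the other moves the treatment difference for reasons unrelated to treatment.

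Exclusion at the analysis stage raises the same issue later, when the arm and possibly the outcome are known, and it conflicts with the intention-to-treat sentence. The age mismatch is a separate and smaller matter: membership of the analysed group for a 65-year-old depends on which list is read.

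**Working it through.** **1. The plan's own figure.** Sample Size gives a target of 44 per arm, 88 in total, and 1.5 enrolled for each subject who meets criteria and finishes. 88 x 1.5 = 132, which reproduces the stated total. The allowance is 132 - 88 = 44, or 44/132 = 33%. It covers failure to meet criteria and failure to finish together, so 44 is only an upper bound on ineligible enrollees. It does show that some are expected.

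**2. The sections side by side.**

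| Question | One place | Another place |
|---|---|---|
| Must inclusion be met? | Yes, at intake or analysis (Inclusion Criteria) | Unenrolment is optional if not met (I. Recruitment) |
| Who may enter? | Everyone admitted to the unit (Exclusion Criteria) | Those who remain eligible (I. Recruitment) |
| Who is analysed? | Those left after exclusions applied at analysis (Exclusion Criteria) | All who completed pre-treatment procedures (I. Recruitment); SAP silent |
| Upper age limit | 64 (Inclusion Criteria) | Excluded only above 65 (Exclusion Criteria) |

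Counted in completed years, a 65-year-old fails inclusion and is not excluded. No other age is affected.

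**3. Is the arm evident when the choice is made?** Study Design has the whole unit on one arm. The standard order is admission, consent, interviews, eligibility decision. That staff know the arm is an inference, but a strong one. Neither document describes concealment or blinding of those who decide. In the remote pathway, interviews precede admission and are repeated only if the gap exceeds 2 months, so the arm running at admission need not be known. That pathway is less exposed.

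**4. How large could the effect be?** The documents give no count of ineligible veterans, no SD, no alpha and no power. Everything in this step is assumed:

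- 44 eligible veterans per arm
- m ineligible veterans kept in one arm and none in the other
- the ineligible differ by d SD in outcome change
- unit SD, no true effect, a two-sided 5% normal test, no covariate

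Bias = d x m/(44 + m). SE = sqrt(1/(44 + m) + 1/44). Rejection rate = Φ(bias/SE - 1.96) + Φ(-bias/SE - 1.96).

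Worked case, m = 10 and d = 0.8: bias = 8/54 = 0.148; SE = sqrt(1/54 + 1/44) = 0.203; ratio = 0.73; rejection = 11.28%.

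Bias in SD, with rejection rate:

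| m | d = 0.3 | d = 0.5 | d = 0.8 |
|---|---|---|---|
| 2 | 0.013 (5.04%) | 0.022 (5.12%) | 0.035 (5.31%) |
| 5 | 0.031 (5.25%) | 0.051 (5.69%) | 0.082 (6.79%) |
| 10 | 0.056 (5.86%) | 0.093 (7.41%) | 0.148 (11.28%) |

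If both arms keep some, the shares partly cancel. With 5 against 3 and d = 0.5, the bias is 0.5 x (5/49 - 3/47) = 0.019 SD.

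**The case against.** The best reply is that the inclusion criteria still bind at analysis. On that reading the discretion concerns only whether a veteran stays enrolled, and someone kept on the study can be left out of the analysis later. CAPS-5 status and age are recorded before treatment, so applying them later need not involve judgement. This is fair as far as it goes, and it means the text does not say that ineligible veterans are analysed. It does not settle the matter. Removal at analysis contradicts the intention-to-treat sentence, the SAP names no analysis set, and nothing requires the person applying the criteria to be unaware of arm or outcome.

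Second, several sections place eligibility review before invitation or consent, and the remote pathway settles it before admission. This stands as a limit on how many veterans are exposed. The discretion sentence, however, is written for those found ineligible after the pre-treatment assessment, and it carries no exception.

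Third, veterans come from a residential PTSD unit, so few may be sub-threshold. That is possible; the documents give no count either way.

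Fourth, the SAP postdates the Protocol and is written in the past tense, so new enrolment wording cannot undo decisions already taken. This stands, and it is why the analysis and reporting part of the fix matters most.

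**Conclusion.** The Protocol contains a stated rule that permits non-uniform selection with the arm evident, and neither document closes it. The sections need to be reconciled. This should be done because it is cheap and because readers otherwise cannot tell whether the two analysed groups were formed alike.

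The size cannot be derived from the documents. On the assumed range above, the bias runs from 0.01 SD, with no practical effect on the error rate, to 0.15 SD, with about 11% rejection at a nominal 5%. It is negligible if selective retentions are few and material only if they are many and one-sided.

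A reader might infer three stronger things that the documents do not support:

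- **That staff did select by arm.** Nothing shows this; the text only allows it.
- **That the age mismatch gives staff discretion, or that the SAP's baseline age difference is a sign of selective retention.** The mismatch is a drafting conflict confined to age 65. An age difference between arms can arise in many ways and says nothing about 65-year-olds. It only makes a clear age rule more useful.
- **That a particular shift in CAPS-5 points follows.** It would need a number of sub-threshold veterans and a difference in their change, and neither document gives one. Nor is any effect shown on the SAS-SR, the other primary outcome.

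**What to change.** 1. **Protocol, I. Recruitment.** Replace the discretionary sentence with one fixed rule for veterans who fail an inclusion criterion. Apply it identically in both arms and base it only on data recorded before treatment (scored CAPS-5, SCID-5, age). Reconcile it with the two statements in Subject Exclusion Criteria that admit everyone on the unit and apply exclusions at analysis.
2. **Protocol, both criteria lists.** State one upper age limit, matching the inclusion criterion. Do not choose it by looking at who was enrolled.
3. **SAP.** Define the primary analysis set by that rule, applied by someone unaware of arm and outcome. Report, by arm and criterion, how many ineligible veterans were kept and how many were unenrolled. Add a sensitivity analysis of all veterans who completed pre-treatment procedures and have outcome data.

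Item 3 remains usable if enrolment has ended.

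**Cost.** A few sentences of wording, one table and one extra analysis. Staff lose discretion over near-threshold veterans, and a few more may become screen failures or fall outside the primary set. The 1.5 enrolment factor already allows for veterans who do not meet criteria.
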